### 2.2 Trial Diagram

Two consecutive run-in cohorts will be treated establishing the safety of neoadjuvant pembrolizumab and pembrolizumab-SRT delivered in the preoperative window. An expansion cohort will include a larger number of patients who will be treated with pembrolizumab alone or be randomized between the two arms.

**Cohort 1:** 6 patients. The patients will undergo 2 cycles of pembrolizumab prior to surgery. Surgery will occur no later than 6 weeks following the last dose of pembrolizumab.

If  $\leq 33\%$  of patients experience grade 3 immune-related toxicity attributable to study interventions (as determined within 30 days of date of surgery), or  $\leq 1$  patient progresses to unresectability over the course of study treatment, proceed to Cohort 2.

If  $>33\%$  of patients experience grade 3 immune-related toxicity attributable to study interventions (as determined within 30 days of date of surgery), or  $> 1$  patient progresses to unresectability over the course of study treatment, the study will terminate.

**Cohort 2:** 6 patients. The patients will undergo 2 cycles of pembrolizumab then within the week (7 days  $\pm$  3 days) following administration of the second cycle, a single fraction of SRT (12 Gy) will be delivered to 50% of the primary tumor only. Definitive surgical resection will occur

[figure not shown]
no later than 6 weeks following the last dose of pembrolizumab.

If  $\leq 33\%$  of patients experience grade 3 immune-related toxicity attributable to study interventions (as determined within 30 days of date of surgery), or  $\leq 1$  patient progresses to unresectability over the course of study treatment, proceed to Expansion Cohort (randomization between parameters of Cohort 1 and Cohort 2, e.g. randomization between preoperative pembrolizumab versus pembrolizumab and SRT).

If >33% of patients in Cohort 2 experience grade 3 immune-related toxicity attributable to study interventions (as determined within 30 days of date of surgery), or > 1 patient progresses to unresectability over the course of study treatment, then proceed to Expansion Cohort (parameters only of Cohort 1, e.g. preoperative pembrolizumab alone).

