**Expansion Cohort:** 28 patients. The patients will be treated according to Cohort 1 if Cohort 2 failed to meet the specified safety milestones. If both cohorts met the safety milestones, then patients in this cohort will be randomized to parameters of either Cohort 1 or Cohort 2. Surgery will occur no later than 6 weeks following the last dose of pembrolizumab.

**Stopping Rule:** If at any point during the study, >15% of patients progress to unresectability over the course of the study treatment, then the study will terminate. This stopping rule will be cumulatively evaluated at all timepoints during the protocol, for all patients enrolled in any phase of the protocol. Each case of study-induced medical unfitness, tumor progression, or any other cause resulting in unresectability will trigger a re-evaluation of the 15% stopping rule.

\* Cycle 2 of pembrolizumab should be given except as recommended per protocol, section 5.2.1.2

\*\* SRT is delivered within 7 days +/- 3 days of second pembrolizumab cycle. If second cycle is not given due to discontinuation, SRT should not be given (patient should continue to surgery)

when deemed safe by treating surgeon).

^ Surgery will take place no later than 6 weeks following last dose of pembrolizumab, e.g. no later than week 7 if only one cycle of pembrolizumab was tolerated, or if two cycles of pembrolizumab were given, week 10.

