#### 3.2 Secondary Objectives & Hypotheses

(1) **Objective:** To assess the safety of preoperative pembrolizumab +/- SRT when combined with surgery;

**Hypothesis:** In patients scheduled for NSCLC resection, pembrolizumab, or pembrolizumab + SRT, given in the preoperative window, will meet safety criteria described by the protocol;

(2) **Objective:** To record the toxicity of preoperative pembrolizumab +/- SRT when combined with surgery, according to CTCAE v. 4, including immune-related adverse events (AEs);

**Hypothesis:** In patients scheduled for NSCLC resection, pembrolizumab, or pembrolizumab + SRT, given in the preoperative window, will result in acceptable short-term and perioperative toxicity;

(3) **Objective:** To determine the 1-year overall survival rate resulting from preoperative pembrolizumab +/- SRT when combined with surgery;

**Hypothesis:** In patients scheduled for NSCLC resection, pembrolizumab + SRT given in the preoperative window will result in a higher 1-year survival rate than pembrolizumab alone;

(4) **Objective:** To determine the 1-year relapse free survival rate resulting from preoperative pembrolizumab +/- SRT when combined with surgery;

**Hypothesis:** In patients scheduled for NSCLC resection, pembrolizumab + SRT given in the preoperative window will result in a higher 1-year relapse free survival rate than pembrolizumab alone;

(5) **Objective:** To determine the 1-year rate of distant metastases resulting from preoperative pembrolizumab +/- SRT when combined with surgery;

**Hypothesis:** In patients scheduled for NSCLC resection, pembrolizumab + SRT given in the preoperative window will result in a lower 1-year distant metastasis rate than pembrolizumab alone;

(6) **Objective:** To assess quality of life associated with preoperative pembrolizumab +/- SRT when combined with surgery;

**Hypothesis:** In patients scheduled for NSCLC resection, pembrolizumab, or pembrolizumab + SRT, given in the preoperative window, will result in acceptable short-term and perioperative quality of life;

(7) **Objective:** To determine the rate of unresectability that results from a program of preoperative pembrolizumab +/- SRT to be followed by a planned surgery;

**Hypothesis:** In patients scheduled for NSCLC resection, either pembrolizumab or pembrolizumab + SRT given in the preoperative window will both result in <15% overall rate of unresectability following the preoperative program;

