#### 7.2 Statistical Analysis Plan

Sample size justification:

The sample size is based upon the anticipated number of patients who will have samples that will be useful for study of immunologic changes in the number of infiltrating CD3+ T cells/ $\mu\text{m}^2$  in the lung cancer tissue between the pre-treatment (baseline) biopsy and post-treatment thoracotomy specimens.

The sample size is fixed at 40 patients. It assumes successful accrual of 6 patients from each of the two run-in cohorts and an additional 28 patients from the randomized expansion cohort, for a total of 40 patients. However, past clinical experience indicates that as many as one-third of patients may not be able to complete a new successful core needle biopsy procedure and only prior archived tissues will be available for any analysis (which may eventually turn out to be insufficient to evaluate for primary endpoint). These patients who enrolled but whose core biopsy is later found to be inadequate after initiation of therapy will be allowed to continue on the protocol but will not be included in the primary endpoint.

The null hypothesis is that a two-fold increase will be seen in 15% of the evaluable 26 patients (assuming up to one third of samples may be unevaluable for primary endpoint). The alternative hypothesis is that a two-fold increase will be seen in 40% of the evaluable 26 patients. This yields 90% statistical power, with one sided 5% alpha level based on an exact binomial test.

The goal of achieving a two-fold increase in 40% of the evaluable population is a reasonable one, as estimated from a previous study showing greater-than-three-fold increase in 57% of patients when CD3+ T cells/ $\mu\text{m}^2$  were measured in prostate cancer tissue treated with a cell- based cancer immunotherapy, with a null hypothesis having been set at a two-fold increase in 15% of the population (Fong 2014). The current study includes immunotherapy +/- stereotactic radiation therapy, both of which are anticipated to create increased immunogenicity against NSCLC.

It is anticipated that accrual will be completed in 10 months (4 patients per month), with each patient treated for approximately 2.5-3 months and then followed for 12 months after completing protocol therapy. Total study duration is 25 months.

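### The 15% unresectability stop has no stated chance of ending the study, conflicts with the run-in rules, and is left out of the printed 90% power

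*Combined protocol and SAP*

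**What the plan says.** Section 2.2 of the combined protocol and SAP (Stopping Rule) ends the study on this condition: "If at any point during the study, >15% of patients progress to unresectability" during study treatment. It adds: "This stopping rule will be cumulatively evaluated at all timepoints during the protocol, for all patients enrolled in any phase of the protocol". Medical unfitness, tumour progression and "any other cause resulting in unresectability will trigger a re-evaluation of the 15% stopping rule". There is no minimum number of patients, no confidence bound and no stated operating characteristic.

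The same section has separate run-in rules for two cohorts of six. For Cohort 1, at most one "patient progresses to unresectability over the course of study treatment, proceed to Cohort 2"; more than one ends the study. For Cohort 2, more than one leads to an expansion with pembrolizumab alone, not to termination.

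Section 3.2, objective 7, hypothesises that the two regimens "will both result in <15% overall rate of unresectability following the preoperative program".

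Section 7.2 says "The sample size is fixed at 40 patients" (6 + 6 + 28). It takes 26 patients as evaluable and tests a 15% null against a 40% alternative: "This yields 90% statistical power, with one sided 5% alpha level based on an exact binomial test". Section 7 does not mention the stopping rule.

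**The concern.** Fifteen percent is both the limit of the rate the protocol hopes to stay under and the line at which it stops. Comparing a raw proportion with that line after every case, from the first patient on, gives chance many opportunities to cross it, above all while the denominator is small. The primary endpoint needs paired biopsy and surgical tissue, so a stop also removes primary data.

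Two things are at stake. The investigators, the DSMC and the IRB cannot see how likely termination is at rates the protocol regards as success. And the printed power describes a trial in which this rule does not operate.

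**Working it through.** **Printed power.** Inputs from section 7.2: n = 26, null 15%, alternative 40%, one-sided 5%, exact binomial. Rejecting at 7 or more responders has alpha 0.083, which is too large. Rejecting at 8 or more has alpha 0.032 and power 0.878. So the named test gives 87.8%, not 90%. The printed figure matches an arcsine approximation at n = 26 (0.900); the exact test first reaches 90% at n = 27 (0.905).

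**Literal stopping rule.** Inputs from section 2.2: stop when cases/patients > 0.15, checked at each case. With patients treated so far as the denominator, the study stops if the 1st case falls by patient 6 (1/6 = 16.7%), the 2nd by 13, the 3rd by 19, the 4th by 26, the 5th by 33 or the 6th by 39. The true rate p is assumed, because the documents give none. An exact patient-by-patient recursion to N = 40, with independent cases, gives:
- P(stop) = 12.2%, 31.1%, 61.4% and 83.5% at p = 2%, 5%, 10% and 15%.
- Share from the first six patients, 1 − (1 − p)^6: 1 − 0.95^6 = 26.5% and 1 − 0.90^6 = 46.9%.
- For comparison, one look at patient 40 (7 or more cases) crosses the line with probability 0.3% at 5% and 10.0% at 10%.

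**Where section 2.2 conflicts.** One case in Cohort 1 is 1/6 = 16.7%: the 15% rule terminates, the run-in rule proceeds. Two cases in Cohort 2 after none in Cohort 1 are 2/12 = 16.7%: the 15% rule terminates, the Cohort 2 rule continues with pembrolizumab alone.

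**Other readings.**
- Enrolled denominator: eight further enrolled patients are counted (assumed; two months at the planned 4 per month), with enrolment capped at 6 and 12 during the run-in.
- Gate first: the Cohort 1 rule governs patients 1–6, and the 15% rule is read only at cases from patient 13. The gate alone stops with probability 1 − (1 − p)^6 − 6p(1 − p)^5, which is 1 − 0.735 − 0.232 = 3.3% at 5% and 1 − 0.531 − 0.354 = 11.4% at 10%.

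**Power allowing for the stop.** If a stopped trial still tests its evaluable patients, power is the sum over n of P(stop at n) × exact-test power at 0.65n patients (rounded down), plus P(no stop) × 0.878. The 65% is 26/40. If a stopped trial cannot test, power is 0.878 × (1 − P(stop)); for example 0.878 × 0.689 = 0.605.

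| Reading | P(stop), p = 5% / 10% | Power, test after a stop | Power, no test after a stop |
|---|---|---|---|
| Literal | 31% / 61% | 64% / 43% | 61% / 34% |
| Literal, 8 more enrolled | 29% / 55% | – | 62% / 39% |
| Gate first, rule from patient 13 | 10% / 41% | 83% / 69% | 79% / 52% |
| Gate first, 8 more enrolled | 4% / 23% | 85% / 76% | 84% / 68% |

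The gate-first rows include the gate's own 3.3% and 11.4%. In the most lenient row the 15% rule itself therefore adds about 1 point at 5% (4.3 − 3.3) and 11 points at 10% (22.7 − 11.4).

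**The case against.** The strongest reply is that the large figures come mainly from reading the 15% rule into the run-in, where the cohort rule says the opposite. That stands: 26.5 of the 31.1 points at 5%, and 46.9 of the 61.4 at 10%, come from one case in the first six. A reader might infer that a regimen meeting the target faces a 31% to 61% chance of being stopped. The documents do not support that without qualification. The true rates are assumed, the run-in rule contradicts the reading, and the stop ends the pooled study rather than one regimen. At a true rate near 5%, honouring the run-in rule leaves the 15% rule with a small effect.

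A second reply is that a strict stop is a legitimate protective choice for patients who could otherwise have curative surgery, and that fixed-sample power is often quoted conditional on completion. Both are fair. A reader might infer that the boundary is wrong and should be loosened. The documents do not settle that: any looser boundary also stops later when the true rate is above 15%. What remains is that the odds are not disclosed, section 7.2 does not say its power is conditional, and even the conditional figure is not 90%.

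Third, section 5.9 replaces patients who leave before surgery without grade 3 or higher toxicity, which could include unresectable patients. The calculation fixes N at 40 without replacement, so its power figures are indicative.

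**Conclusion.** The point holds in limited form. The protocol has an unquantified study-wide stop whose chance of operating depends heavily on which part of section 2.2 governs the run-in: 31% and 61% on the literal text, and down to 4% and 23% on the most lenient reading, at assumed true rates of 5% and 10%. Near 10%, which the protocol would count as success, the chance is material on every reading.

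The conditional power is 87.8%. Allowing for the stop and still testing, it ranges from 64% to 85% at 5% and from 43% to 76% at 10%. These figures assume independent cases, 65% evaluable, unresectability independent of CD3+ response, N fixed at 40 and no replacement. The documents do not say whether the primary test is run after a stop, so no single unconditional power can be given as the trial's true power.

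**What to change.** 1. **Section 7.2.** Restate the power as 87.8% for 26 evaluable patients (reject at 8 or more, alpha 0.032), conditional on the trial not being terminated under section 2.2. Add a short table of termination probability and unconditional power over a range of true unresectability rates. State the denominator, the replacement assumption, and whether the primary test is run after a stop.
2. **Section 2.2.** Reconcile the run-in rules with the 15% stopping rule, for Cohort 1 (1 of 6) and Cohort 2 (2 of 12), so that one rule plainly governs each stage. The sponsor and DSMC should decide, with these probabilities in view, whether the boundary stays as it is.

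Item 1 costs a few sentences and a table, and the stated power becomes less favourable. Item 2 needs a protocol amendment with DSMC agreement. Neither adds patients or procedures.

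### Section 2.2 gives opposite instructions for the same run-in result: one unresectable patient of six means both proceed and terminate

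*Combined protocol and SAP*

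**What the plan says.** Section 2.2 (Trial Diagram) contains two sets of rules on unresectability.

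**Run-in gates, six patients per cohort.** In Cohort 1, at most one unresectable patient leads to the instruction "patient progresses to unresectability over the course of study treatment, proceed to Cohort 2". More than one leads to "patient progresses to unresectability over the course of study treatment, the study will terminate". In Cohort 2, at most one leads to "proceed to Expansion Cohort (randomization between parameters of Cohort 1 and Cohort 2", and more than one leads to "then proceed to Expansion Cohort (parameters only of Cohort 1, e.g. preoperative pembrolizumab alone". In every one of these sentences the unresectability limb is tied to a 33% limit on grade 3 immune-related toxicity by the same connector: "attributable to study interventions (as determined within 30 days of date of surgery), or".

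**Stopping Rule, whole study.** The study terminates "If at any point during the study, >15% of patients progress to unresectability over the course of the study treatment". On scope: "This stopping rule will be cumulatively evaluated at all timepoints during the protocol, for all patients enrolled in any phase of the protocol". On timing: "Each case of study-induced medical unfitness, tumor progression, or any other cause resulting in unresectability will trigger a re-evaluation of the 15% stopping rule". No minimum number of patients is set, and nothing says how this rule relates to the gates.

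Three other sections bear on the point:
- Section 5.8 requires discontinuation for confirmed radiographic progression.
- Section 5.9 replaces patients who drop out before pembrolizumab, and those who leave before surgery without grade 3 or higher toxicity.
- Section 5.10 lists criteria for early termination and refers to neither set of rules.

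**The concern.** A gate that tolerates one event in six cannot be followed alongside a standing limit that one event in six already exceeds. Both rules describe the event as progression to unresectability during study treatment, so a difference in endpoint does not explain the mismatch.

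At stake is whether the study continues after Cohort 1. After Cohort 2 it is whether expansion is randomized, runs on Cohort 1 treatment only, or does not start. In the affected outcomes, following one sentence of Section 2.2 means departing from another, and the choice would be made with the results already known.

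The *or* adds a second problem inside the gates. A cohort can satisfy the favourable sentence on one limb and the unfavourable sentence on the other.

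**Working it through.** **Inputs.** Cohort sizes are 6, 6 and 28 (Sections 2.2 and 7.2), and 6 + 6 + 28 = 40 matches the stated total. The gate allows at most 1 unresectable patient per run-in cohort. The stopping limit is above 15%, read at every case. The plan gives no operating characteristics for either rule, so there is no figure of its own to reproduce beyond the total of 40.

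**Step 1: gates against Stopping Rule, planned enrolment, no replacements.**

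- Cohort 1, one case: 1/6 = 16.7%, above 15%. A case before the sixth patient enrols gives a larger fraction. The gate says proceed; the Stopping Rule says terminate.
- Cohort 1 clear, one case in Cohort 2: 1/7 = 14.3% down to 1/12 = 8.3%. No breach and no conflict.
- Cohort 1 clear, second case in Cohort 2: 2/8 = 25.0% down to 2/12 = 16.7%. Always above 15%. The gate says expand on Cohort 1 treatment; the Stopping Rule says terminate.
- One case in each cohort: the Stopping Rule was already met in Cohort 1.

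**Step 2: the gates against themselves.** A cohort of six has 7 × 7 = 49 combinations of toxicity count and unresectability count. Taking 33% literally, 2/6 = 33.3% is over the limit. Toxicity is then within the limit for 2 counts (0–1) and over it for 5 (2–6). Unresectability splits the same way, 2 and 5. Combinations that meet both sentences: 2 × 5 + 5 × 2 = 20. If 33% means one third, toxicity splits 3 and 4, giving 3 × 5 + 4 × 2 = 23. None meets neither sentence. Example in Cohort 1: 3 of 6 with grade 3 toxicity and 0 of 6 unresectable meets both the proceed and the terminate sentence, and the 15% rule does not settle it.

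**Step 3: replacement.** The unresectable patient may be one whom Section 5.9 replaces. If replaced patients stay in the denominator and the rule is read after replacement, 1/7 and 2/14 are both 14.3%, under the limit. Read at the case, before that patient's replacement enrols, the fraction is at least 1/6 in Cohort 1. At a second case in Cohort 2 it is at least 2/13 = 15.4%, even with the first case's replacement counted. Only counted replacements for other reasons would lower these.

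**Step 4: how often.** The documents give no expected rate. Assume a true rate p of 2%, 5% or 10%, all under the 15% of secondary hypothesis 7, with independent patients, the toxicity criterion met and no replacements. With the limbs read as *and*:

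P(conflict) = P(exactly 1 of 6) + P(0 of 6) × P(2 or more of 6), where P(0 of 6) = (1 − p)^6 and P(exactly 1 of 6) = 6p(1 − p)^5.

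The literal *or* makes 2 or more of 6 in Cohort 1 contradictory too, so its probability is added in the last column.

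| p | P(0) | P(1) | P(≥2) | P(0) × P(≥2) | Gates against Stopping Rule | Any contradiction, literal *or* |
|---|---|---|---|---|---|---|
| 2% | 0.8858 | 0.1085 | 0.0057 | 0.0050 | 0.1135 | 0.1192 |
| 5% | 0.7351 | 0.2321 | 0.0328 | 0.0241 | 0.2562 | 0.2890 |
| 10% | 0.5314 | 0.3543 | 0.1143 | 0.0607 | 0.4150 | 0.5293 |

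**The case against.** The strongest reply is that the Stopping Rule is a standing, study-wide limit placed over the cohort gates, and the stricter instruction binds. Its wording on scope supports that reading, under which the Cohort 1 allowance is redundant rather than contradictory. But no precedence is written. On that reading the allowance of one in Cohort 1, and the unresectability route to pembrolizumab-alone expansion, have no effect at planned enrolment (the toxicity route remains). A rule that can never operate still needs correcting.

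On the *or*, Section 2.1 speaks of cohorts meeting safety parameters in the plural, and the Expansion Cohort paragraph speaks of milestones. Both suggest that *and* was meant in the favourable sentences. That is a fair inference, and it makes the last column of the table the weaker figure. Reading *and* leaves the main conflict untouched.

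Two further limits stand. The statements about every first case in Cohort 1 and every second case in Cohort 2 hold at planned enrolment. One counted replacement for another reason, such as a drop-out before pembrolizumab, would bring a first case to 1/7 = 14.3%. And the trial diagram is not reproduced in this copy, so the point concerns the written text only. The primary test and its error rate are unaffected.

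**Conclusion.** The concern holds and must be fixed. As written, Section 2.2 gives opposite instructions for 1 of 6 unresectable in Cohort 1, and for 0 of 6 followed by 2 or more of 6 in Cohort 2. These two conflicts rest only on the stated cohort sizes and thresholds, without counted replacements.

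The probabilities of 11.4%, 25.6% and 41.5% depend on the assumed rates and show only that the affected outcomes are not remote. Most of that probability is the single case in Cohort 1: 10.8%, 23.2% and 35.4%. The *or* overlap is a second defect in the same sentences and raises the totals to 11.9%, 28.9% and 52.9% if read literally. Whether a breach exists at all can also turn on an undefined denominator and an unstated time of reading.

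**What to change.** Reconcile the gates with the Stopping Rule so that each run-in outcome in Cohorts 1 and 2 has one stated consequence. Specifically:

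- State which rule governs during the run-in, or how the two combine.
- Settle the connector between the toxicity and unresectability limbs in the favourable sentences.
- Define the denominator: enrolled patients or those whose surgical outcome is known, and whether patients replaced under Section 5.9 count. State when the fraction is read relative to replacement.
- Express the reconciled rule as event counts by number of patients. For reference, the present 15% limit is exceeded by one case up to 6 patients, by two up to 13 and by three up to 19.
- Cross-refer to the rule from Section 5.10.

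The threshold, and which rule prevails, are for the sponsor and investigators to decide. The cost is protocol wording, a short table and one cross-reference, with no added patients or procedures.

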#### Holding Study Interventions:

When study interventions are administered in combination, if the AE is considered immune-related, both interventions should be held according to recommended dose modifications.

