### **5.9 Subject Replacement Strategy**

Patients who drop out before starting pembrolizumab will be replaced. In addition, patients who come off study before completing surgery without grade  $\geq 3$  toxicity will be replaced. The frequency of each of these events will be reported and reasons for replacement reviewed.

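### The Cohort 2 safety gate has no SRT-exposure condition, so SRT can be cleared for randomisation on fewer than six SRT-treated patients

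*Combined protocol and SAP*

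**What the plan says.** Section 2.2 of the combined protocol and SAP gives the purpose of the run-in: "Two consecutive run-in cohorts will be treated establishing the safety of neoadjuvant pembrolizumab and pembrolizumab-SRT delivered in the preoperative window". Cohort 2 is "6 patients. The patients will undergo 2 cycles of pembrolizumab then within the week" of the second dose a single SRT fraction. Its gate is worded by cohort membership: "If >33% of patients in Cohort 2 experience grade 3 immune-related toxicity" attributable to the study interventions, counted to 30 days around surgery, or if more than one patient becomes unresectable, the expansion uses pembrolizumab alone. Otherwise SRT enters the randomised part. Neither limb asks whether SRT was given.

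The schema note in the same section covers a patient who stops after cycle 1: "If second cycle is not given due to discontinuation, SRT should not be given", and the patient continues to surgery when the surgeon judges it safe. Sections 5.2 and 6.2.10 repeat the rule on SRT.

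Section 5.9 replaces two groups: those who drop out before starting pembrolizumab, and "patients who come off study before completing surgery without grade" 3 or higher toxicity. Sections 7.1 and 7.2 assume six patients per run-in cohort and add no rule for the gate. In section 7.2, evaluable refers to tissue for the primary endpoint.

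**The concern.** The Cohort 2 gate is the only step that decides whether SRT is randomised. Read together, the sections allow a Cohort 2 patient to receive pembrolizumab only, have surgery, stay among the six and not be replaced.

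This can happen without a gate event. Table 3 of section 5.2.1.1 withholds pembrolizumab for several grade 2 immune-related events and allows it to resume after a steroid taper of at least 4 weeks. The same section discontinues treatment after more than 14 days' interruption for toxicity unless the investigators agree otherwise. A grade 2 event after cycle 1 can therefore cancel cycle 2, and SRT with it, while adding nothing to a count of grade 3 events.

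At stake is the evidence behind secondary objective 1 (safety) for the combination. The gate would appear to rest on six patients when it might rest on five or four.

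**Working it through.** The documents give no operating characteristics for this gate, so there is no stated figure to reproduce. The calculations cover the toxicity limb only.

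**Inputs.** From section 2.2: cohort size 6 and the 33% cut-off. Assumed: true gate-event rate p = 40% in SRT-treated patients; event rate u in patients without SRT (0 unless stated); omission rate q = 5%, 10% or 20% per patient. The documents give no omission rate.

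**1. Cut-off.** 2/6 = 33.3% exceeds a literal 33%, so at most 1 event passes (c = 1). If 33% is meant as one third, 2 events pass (c = 2). Both are shown.

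**2. Passing, given m of 6 exposed and u = 0.** P(pass) = P(Bin(m, 0.4) ≤ c).
- m = 6, c = 1: 0.6^6 + 6(0.4)(0.6^5) = 0.047 + 0.187 = 0.233
- m = 5, c = 1: 0.6^5 + 5(0.4)(0.6^4) = 0.078 + 0.259 = 0.337
- m = 4, c = 1: 0.6^4 + 4(0.4)(0.6^3) = 0.130 + 0.346 = 0.475
- c = 2 adds C(m,2)(0.4^2)(0.6^(m−2)), giving 0.544, 0.683 and 0.821.

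**3. How often omissions occur.** P(at least one of six) = 1 − (1 − q)^6.

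**4. Average over omissions.** With u = 0, each enrolled patient has event probability 0.4(1 − q) = 0.38, 0.36 or 0.32. P(pass) = P(Bin(6, that value) ≤ c).

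| Omission rate q | At least 1 of 6 without SRT | At least 2 of 6 | P(pass), c = 1 | P(pass), c = 2 |
|---|---|---|---|---|
| 0 | 0 | 0 | 23% | 54% |
| 5% | 26.5% | 3.3% | 27% | 59% |
| 10% | 46.9% | 11.4% | 30% | 63% |
| 20% | 73.8% | 34.5% | 38% | 71% |

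**5. Dependence on u.** With five exposed and c = 1, P(pass) = (1 − u)(0.337) + u(0.078).
- u = 0: 34%
- u = 9.5% (the grade 3 or higher rate quoted for KEYNOTE-001 in section 4.1.2, a different setting): 31%
- u = 40%: 23%, the same as six exposed
- u = 100%: 8%

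With c = 2, u = 0, 40% and 100% give 68%, 54% and 34%.

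**6. Does the denominator alone change a decision?** At a literal 33%, 2/6, 2/5 and 2/4 all fail, and 1/6, 1/5 and 1/4 all pass, so it does not with four or more exposed. At one third it does: 2/6 passes while 2/5 = 40% and 2/4 = 50% fail.

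**7. Information lost.** With zero events, the one-sided 95% upper bound 1 − 0.05^(1/m) is 39.3% for six exposed, 45.1% for five and 52.7% for four.

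**The case against.** The strongest defence is that the whole-cohort count is the right one. The expansion randomises to the Cohort 2 regimen with the same rule for omitting SRT, so toxicity among all six describes the strategy that will be randomised. This is a fair reading for judging the strategy. It does not meet the purpose stated in section 2.2, which is to establish the safety of pembrolizumab with SRT delivered, and it leaves the exposed number without a floor.

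Four stronger readings are tempting, and the documents do not support them:
- **That two events among four treated patients would pass as 2/6.** Under the literal cut-off 2/6 fails, so the example works only if 33% means one third.
- **That the gate is always biased towards proceeding.** A grade 3 immune-related event after cycle 1 counts against the gate although no SRT was given. Step 5 shows that the direction depends on u.
- **That any immune-related hold after cycle 2 produces an unexposed patient.** Section 5.2.1.1 says "if the AE is considered immune-related, both interventions should be held according to recommended dose modifications", but it also allows the combination to restart. Only a missed second cycle is expressly routed to surgery without SRT.
- **That no unexposed patient is ever replaced.** A patient who leaves before surgery without grade 3 or higher toxicity is replaced. Section 5.8 also requires discontinuation from the trial for intercurrent illness that prevents further protocol treatment, which is hard to square with the section 2.2 instruction to continue to surgery.

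It also stands that the figures for four exposed need two omissions, which has a probability of 3.3% at 5% omission and 11.4% at 10%. The cumulative stopping rule, adverse-event review and early-termination criteria continue to apply, but none sets a toxicity threshold for SRT.

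**Conclusion.** The point holds in a limited form. Followed as written, the gate can open SRT for randomisation on fewer than six SRT-treated patients. No sentence says outright that unexposed patients count. It follows from the cohort-based denominator, the narrow replacement rule and the absence of an evaluability definition.

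The gate is looser when omissions come without a gate event. At 5% to 10% omission, the averaged chance of passing at a true 40% rate rises by about 3 to 7 points if at most one event passes (23% to 27% or 30%). If two pass, it rises by about 4 to 8 points (54% to 59% or 63%). At 20% omission it reaches 38% and 71%. These figures rest on the assumed 40% rate, the assumed omission rates and no events in unexposed patients. A higher u shrinks the effect and, above 40%, reverses it.

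The gate remains usable, but the text does not secure its claim to have tested SRT in six patients. The amendment is worth making because it is cheap.

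**What to change.** In section 2.2, define the Cohort 2 gate set as the first six patients who either received SRT or had a gate event without having received it. A gate event is qualifying toxicity within the existing 30-day post-surgery window, or unresectability. A patient who completes that window without SRT and without a gate event stays in the trial and in all analyses, but the next enrolled patient is also assigned to Cohort 2 and the expansion cohort is reduced by one. Report the number of SRT-treated patients alongside the gate decision. Cross-refer to this in section 5.9.

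If unexposed patients have no events, this restores the six-exposed figures (23% or 54%). If some do, their events count while their event-free counterparts do not, so the rule is somewhat stricter than six exposed patients would give.

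Cost: a short addition to the text and no change to any dose, schedule or treatment rule. The total stays 40 and the pooled primary test keeps its planned size. Possibly one or two fewer patients are randomised, so with blocks of four the last block is incomplete (28 − 1 = 27 or 28 − 2 = 26) and the arms can differ by at most two. The Cohort 2 decision waits for the added patient's course. At the protocol's outer limits this is about 13 weeks (3 weeks to cycle 2, up to 6 weeks to surgery, then 30 days), and less if surgery is as prompt as section 2.1 expects.
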